REDUCING TINNITUS SYMPTOMS**

THIS STUDY INVOLVES 8 WEEKS OF SELF-ADMINISTERED LASER LIGHT PROCEDURES WITH THE ERCHONIA® HLS™ LASER AT YOUR HOME

FOR MORE INFORMATION PLEASE CONTACT:

<PI name>
<test site name & location>
<phone # and/or e-mail>

b) Newspaper Ad

**Tinnitus
Research Study**

This study is to see if the Erchonia® HLS™, a non-invasive, investigational device that uses low-level laser light, can help to relieve tinnitus that has been ongoing for at least 6 months.

The study involves 8 weeks of self-administered at home treatments.

Please contact <PI name> at
<test site name & location> at
<phone and/or e-mail> for details.

Compensation

A subject will not receive financial compensation for his or her participation in this clinical study.

A subject will not be charged for the cost of the study procedures with the Erchonia® HLS™ Laser or for the cost of any other directly-related evaluations or measurements that occur as part of his or her participation in the study.

Sample size

There will be 10 qualified subjects enrolled in this pilot study, all receiving active procedures. 5 subjects will be assigned to Group A and 5 subjects to Group B.

STUDY PROCEDURE

STUDY TEST BATTERY

The following is a list and description of the study assessment tools to be used and the variables to be recorded in this clinical study. At each evaluation point, the precise tools and variables from this list that will be employed will be specified.

BASELINE VARIABLES

A. *Tinnitus Variables*

- Diagnosed etiology of tinnitus, if known. *Responses:* presbyacusis, noise-induced, unknown.
- Number of months/years since tinnitus onset.
- Location of tinnitus. *Responses:* unilateral - right ear, unilateral - left ear, bilateral - both ears, nonspecific (generally inside the head).

B. *Medication and Treatment*

- *Prior treatment approaches for tinnitus reduction:* Record all prior treatments, whether conventional or alternative, tried by the subject for tinnitus reduction.
- *Concomitant Medication and Therapy Use:* Record all over-the-counter and prescription medications currently used for any indication (other than the management of tinnitus symptoms)

C. *Subject Demographics:* Subject age, gender and ethnicity are recorded.

OUTCOME ASSESSMENT TOOLS

PRIMARY OUTCOME MEASURE:

Tinnitus Handicap Inventory (THI)

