The Tinnitus Handicap Inventory (THI) (Newman et al, 1996, Newman et al, 1998) is a 25-item self-report questionnaire that has Functional, Emotional and Catastrophic subscales. It has excellent convergent validity, construct validity and test-retest reliability. The THI takes 10 minutes to complete.

The individual responses to each of the 25 items are recorded as follows:

- ✓ Yes: 4
- ✓ Sometimes: 2
- ✓ No: 0

Individual scores for each question are added for the total THI score ranging from 0 to 100.

Another way of looking at the results of the THI is by Grade determination, as follows:

- *Grade 1 - slight - (THI 0-16)* – Tinnitus only heard in quiet environment, very easily masked. No interference with sleep or daily activities; generally pertains to individuals who are experiencing but are not troubled by tinnitus.
- *Grade 2 - mild - (THI 18-36)* – Tinnitus easily masked by environmental sounds and easily forgotten with activities. May occasionally interfere with sleep but not daily activities.

- *Grade 3 - moderate - (THI 38-56)* – Tinnitus may be noticed even in the presence of background or environmental noise although daily activities may still be performed. Less noticeable when concentrating. Not infrequently interferes with sleep and quiet activities.
- *Grade 4 - severe - (THI 58-76)* – Tinnitus almost always heard, rarely if ever masked. Leads to disturbed sleep pattern and can interfere with ability to carry out normal daily activities. Quiet activities adversely affected. Hearing loss is likely present, but its presence is not essential.
- *Grade 5 - catastrophic - (THI 78-100)* - All tinnitus symptoms at level of severe or worse. Should be documented evidence of medical consultation. Hearing loss is likely present, but its presence is not essential. Associated psychological pathology is likely to be found in hospital or general practitioner records. Given the epidemiological data, grading in this group should be extremely rare.

SECONDARY OUTCOME MEASURES:

Numerical Rating Scale (NRS)

The Numerical Rating Scale (NRS) will be used to capture the self-reported daily impact of Tinnitus Annoyance and Tinnitus Loudness. Zero represents 'no impact at all' whereas the upper limit represents 'the worst impact ever possible'.

NUMERICAL SCALE: TINNITUS ANNOYANCE

How does the subject rate his or her tinnitus annoyance on a scale of 1 to 100? With 1 being "No Annoyance" and 100 being "Worst possible Annoyance".

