A subject who satisfies any of the following criteria will be excluded from study participation:

- Objective tinnitus
- Atonal, pulsatile, intermittent, or occasional tinnitus
- Severe or profound hearing loss in one or both ears
- Current or prior surgically removed acoustic neuroma
- Consistent use of any of the following drugs known to cause or increase tinnitus (primarily ototoxins) within the past 30 days:
 - ✓ NSAIDS (motrin, naproxen, relafen, etc)
 - ✓ aspirin (exceeding 300mg per day) and other salicylates
 - ✓ Lasix and other "loop" diuretics
 - ✓ "mycin" antibiotics such as vancomycin
 - ✓ quinine and related drugs
 - ✓ Chemotherapy agents such as cis-platin
- Acute or chronic vertigo/dizziness
- Ménière's disease
- Prior stapedectomy
- Prior mastoidectomy
- Auditory nerve tumor (acoustic neuroma), current or surgically removed in the past
- Active infection/wound/external trauma to the areas to be treated with the laser
- Medical, physical or other contraindications for, or sensitivity to, light therapy
- Pregnant, breast feeding, or planning pregnancy prior to the end of study participation
- Developmental disability or cognitive impairment that in the opinion of the investigator would preclude adequate comprehension of the informed consent form and/or ability to record the necessary study measurements

INCLUSION CRITERIA PART 2

- Total THI score is **38 (Grade 3) or greater.**
- Numerical Rating Scale (NRS): Tinnitus Annoyance is **40 out of 100 or greater.**
- Numerical Rating Scale (NRS): Tinnitus Loudness is **40 out of 100 or greater.**

SUBJECT GROUP ASSIGNMENT

A fully qualified subject is assigned by the investigator to Procedure Group A or to Procedure Group B.

PRE-PROCEDURE EVALUATION PHASE

The pre-procedure evaluation phase commences following successful study qualification, on the same day or another day. During pre-procedure evaluation, the following is recorded over videoconference or telemedicine:

BASELINE VARIABLES

- Tinnitus Variables
- Medication and Treatment

- Subject Demographic

[figure not shown]
PROCEDURE ADMINISTRATION PHASE

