The qualified subject will be shipped a Erchonia® HLS™ device, that is preset and cannot be altered by the end user. Additionally, the subject will be shipped Erchonia® HLS™ Operation Manual and Treatment Log Form that corresponds to the subject's assigned treatment group (A or B). The procedure administration phase lasts 8 weeks and comprises 56 procedure administrations with the Erchonia® HLS™ administered by the subject at home: daily procedure administrations for 8 weeks.

PROCEDURE ADMINISTRATION PROTOCOL

- The procedure administration phase of the study commences following completion of the pre-procedure phase, on the same day or up to 15 days later.
- The procedure administration phase extends over 8 consecutive weeks.
- Each subject receives 56 total procedures with the Erchonia® HLS™: daily procedure administrations for 8 weeks.
- Each procedure administration lasts 10 minutes.
- Each procedure administration is completed at the subject's home.
- Each subject will be provided an at home "Operation Manual" that details the laser use and treatment administration.
- Each subject will be provided at home "Treatment Log Forms" to document each time the treatment is administered.

- **Group A: Procedure administration protocol is as follows:**
 1. The subject is correctly fitted with the provided safety goggles.
 2. The Erchonia® HLS laser is held at approximately 4 inches from the skin throughout the entire treatment.
 3. The Erchonia® HLS™ is then activated for 5 minutes.
 4. The laser treatment begins approximately 1 inch above the right ear and applied in a slow continuous sweeping motion down the right side of the neck and then proceed back to top of ear. This back and forth sweeping motion is performed for 5 continuous minutes.

[figure not shown]
5. Step 4 is then repeated over the left side of head and left side of neck. Both the right and left side will receive 5-minute treatment each.
6. The subject's protective eyewear is then removed, and the session is over.

➤ **Group B: Procedure administration protocol is as follows:**

- This is an alternating treatment protocol, such as the subject will apply the laser treatment to the head on days 1 and 2, and on day 3 the laser is applied to the midsection. This 3-day rotation is followed throughout the 8 weeks and is detailed in the subjects “Treatment Log Forms”.
 1. The subject is correctly fitted with the provided safety goggles.

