2 WEEK EVALUATION

Following 2 weeks of study procedure administrations with the Erchonia® HLS™, the following will be recorded over videoconference or telemedicine with the site investigator and subject:

- Numerical Rating Scale (NRS): Tinnitus Loudness
- Numerical Rating Scale (NRS): Tinnitus Annoyance
- Tinnitus Handicap Inventory (THI)
- Adverse Events Evaluation

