8 WEEK EVALUATION: STUDY ENDPOINT

Following 8 weeks of study procedure administrations with the Erchonia® HLS™, the following will be recorded over videoconference or telemedicine with the site investigator and subject as outlined in the STUDY TEST BATTERY section above. These recordings will form the study endpoint data set from which change from baseline will be evaluated with respect to assessing study outcome.

- Tinnitus Handicap Inventory (THI)
- Numerical Rating Scale (NRS): Tinnitus Loudness
- Numerical Rating Scale (NRS): Tinnitus Annoyance
- Subject Satisfaction With Study Outcome
- Adverse Events Evaluation

ADVERSE EVENTS

At any time throughout the duration of the clinical trial that is necessary, any and all potential adverse events reported by a subject will be reported to the investigator and will be recorded on the case report form, and subsequently evaluated by a suitably qualified independent reviewer for determination of relationship to the study treatment and whether or not any corrective action needs to be taken. All potential adverse events recorded will be appropriately reported to the governing IRB, as applicable.

It is unlikely and not expected that any adverse events will result from implementation of this clinical study protocol. Prior clinical trials using low level laser light have not typically yielded any adverse events or reactions. However, potential adverse events that may feasibly occur from application of

the Erchonia® HLS™ include, but are not necessarily limited to: skin irritation, discoloring, rash, indentations and infection.

PRIVACY AND CONFIDENTIALITY

Records for each subject in this clinical study will be maintained in separate files in a locked filing cabinet at the respective test site. The investigator at the test site will be responsible for ensuring that all records for a subject pertaining to his or her participation in the clinical study are maintained in the subject's file at all times other than when information is being recorded on them.

Copies of all subject case report forms will be made and supplied to Regulatory Insight, Inc. and Erchonia Corporation. Regulatory Insight, Inc. and Erchonia Corporation will maintain these copies in a separate clinical study file that is kept in a locked filing cabinet on their respective premises. The original records will be maintained at the respective test sites.

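### THI and both NRS ratings are thresholded at entry and not scheduled again before treatment, so the before-after change is expected on average to include some regression to the mean

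*Combined protocol and SAP*

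**What the plan says.** - **Entry** (INCLUSION CRITERIA PART 2): "Total THI score is 38 (Grade 3) or greater", and NRS annoyance and NRS loudness must each be at least 40 out of 100.
- **Rule for reading the schedule** (STUDY TEST BATTERY): "At each evaluation point, the precise tools and variables from this list that will be employed will be specified".
- **After qualification** (PRE-PROCEDURE EVALUATION PHASE): "The pre-procedure evaluation phase commences following successful study qualification, on the same day or another day". The items listed are tinnitus variables, medication and treatment, and demographics. The BASELINE VARIABLES list in STUDY TEST BATTERY has the same three headings. Neither list contains THI or NRS.
- **Start of treatment** (PROCEDURE ADMINISTRATION PROTOCOL, first bullet): "The procedure administration phase of the study commences following completion of the pre-procedure phase, on the same day or up to 15 days later". No repeat THI or NRS is listed.
- **Next readings** (2 WEEK EVALUATION): "Following 2 weeks of study procedure administrations with the Erchonia® HLS™, the following will be recorded over videoconference or telemedicine", with THI and both NRS ratings on the list.
- **Outcome contrast** (8 WEEK EVALUATION: STUDY ENDPOINT): "These recordings will form the study endpoint data set from which change from baseline will be evaluated with respect to assessing study outcome". STATISTICAL ANALYSIS, under Evaluation Time Points, names a pre-treatment baseline as one of the four time points.
- **Control** (SUBJECT GROUPS): both groups use the active device.

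**The concern.** If the reading that admits a subject is also the baseline, the admitted subjects include some whose error on that day happened to be upward. Their later readings then fall on average even if the device does nothing. EXPECTED RESULTS anticipates a change in the same direction. No untreated or sham group would show how much of a fall to discount.

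At stake is the descriptive change from baseline on THI and both NRS ratings. STATISTICAL ANALYSIS says the results may help in developing a controlled study, so an optimistic before-after figure could carry into its planning.

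**Working it through.** **1. Schedule.** THI and NRS are placed at qualification and at Weeks 2, 4 and 8. Both text lists for the period between qualification and treatment omit them, yet a pre-treatment baseline is required. The qualifying scores are the only scheduled readings that can fill that role. This is an inference: no sentence says so, and one figure next to the pre-procedure list was not available.

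**2. Inputs.** From the protocol: cut-offs 38, 40 and 40; 10 subjects, 5 per group. THI reliability is described only in words: "It has excellent convergent validity, construct validity and test-retest reliability". No mean, SD, reliability coefficient or screening rate is given, so there is no planned figure to reproduce. Assumed:
- SD 22 on each scale.
- Source means (THI/NRS) 35/50, 45/50, 55/50, 55/60 and 65/70.
- THI reliability r of 0.9 or 0.7; NRS reliability 0.6 or 0.8.
- True-score correlation 0.6 between THI and NRS, and 0.7 between the two NRS ratings.
- Follow-up errors independent of qualifying errors.

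**3. Closed form, THI cut-off alone.** Expected fall = (1 − r) × SD × φ(a)/(1 − Φ(a)), with a = (38 − mean)/SD. For mean 45, a = −7/22 = −0.318, the ratio is 0.607, and 22 × 0.607 = 13.4. The fall is 0.1 × 13.4 = 1.3 points at r = 0.9 and 0.3 × 13.4 = 4.0 at r = 0.7. It is zero only if r = 1, and close to zero if nearly all candidates already exceed the cut-off.

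**4. Simulation, all three cut-offs, scores bounded and rounded to their scales, no device effect.** With independent errors the THI falls are smaller than in step 3, because passing the NRS cut-offs also selects for higher true THI.

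| Errors across the three scales | Source THI mean | THI fall, r = 0.9 | THI fall, r = 0.7 |
|---|---|---|---|
| Independent | 35–55 | 0.4–1.5 | 1.4–4.5 |
| Independent | 65 | about 0.3 | about 1.0 |
| Correlated 0.5 | 35–55 | 1.1–2.6 | 2.7–6.2 |
| Correlated 0.5 | 65 | 0.6–0.8 | 1.5–1.8 |

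The top of each range needs a source mean of 35, which is below the cut-off. For source THI means 35–55, each NRS falls 0.9–3.5 points with independent errors, and by up to about 5.7 if errors correlate 0.5.

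**5. Scale against sampling error.** SD of change is about 22 × √(2(1 − r)): 9.8 at r = 0.9 and 17.0 at r = 0.7. Dividing by √10 gives 3.1 and 5.4; dividing by √5 gives 4.4 and 7.6. In the selected, bounded sample the standard errors are slightly smaller: about 3 and 5 at n = 10, and about 4.3 and 7.2 at n = 5.

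At n = 10 with independent errors, the largest ratios are 1.5/3.1 ≈ 0.5 and 4.5/5.1 ≈ 0.9. With correlated errors they are 2.6/3.0 ≈ 0.9 and 6.2/5.1 ≈ 1.2. At n = 5 the largest is 6.2/7.2 ≈ 0.9.

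**6. Effect of an unthresholded second reading.** The share of the shift that remains is roughly the correlation between its error and the qualifying error: about 0 at correlation 0 and about half at 0.5. At 0.5, for source THI means 35–55 and independent errors across scales, 0.2–0.8 THI points remain at r = 0.9 and 0.7–2.3 at r = 0.7.

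**The case against.** The strongest reply is that this is an open-label, uncontrolled pilot of 10 subjects with no success criteria. Placebo response and natural course will affect the change whatever is done about baseline, and the expected shift is usually smaller than the sampling error. It may be smaller still. Recruitment is from people in or seeking treatment, or answering an advertisement, so many may already exceed the cut-offs, and the THI is described as highly reliable. The planned display of all time points already lets a reader see the change from Week 2 to Week 8.

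Most of this stands, and it limits the consequence. It does not remove the point. Sampling error can go either way and shrinks with more subjects; this shift favours improvement on average and does not shrink. Descriptive change is the main planned output, since the ANCOVA is optional. A separate baseline reading may be intended, but the text does not schedule one, so clarification is needed in either case.

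A reader might infer that any observed improvement would be an artefact, or that a formal test is biased. The documents support neither: the expected shift is small on most assumptions, the observed change in 10 subjects could go either way, and no formal success test is planned. A reader might also infer that the comparison of Groups A and B is distorted. Both groups face the same cut-offs, so that contrast is less affected; in simulation with assignment unrelated to score, the mean difference in change was within 0.15 points of zero. Satisfaction has no baseline and is unaffected.

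**Conclusion.** The point holds as a limited design weakness. On the schedule as written, the qualifying THI and NRS scores serve by inference as baseline, and the before-after change on these scales is expected on average to include some regression to the mean. The direction requires only that reliability is below 1 and that the cut-offs exclude some candidates.

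The size rests wholly on assumed inputs and on whether errors are shared across the three self-reports. Shared errors are plausible, because the scales are recorded at the same evaluations. It would therefore go too far to say that the shift is always below one standard error: at r = 0.7, a source mean of 35 and error correlation 0.5, it reaches about 1.2 standard errors at n = 10. It would equally go too far to call it large, since at r = 0.9 it stays below one standard error in every scenario examined. The change is worth making because it is cheap, not because the study fails without it.

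**What to change.** Add THI, NRS loudness and NRS annoyance to the pre-procedure evaluation videoconference, with no second threshold. Hold that evaluation on a different day from qualification, which the protocol already permits, and before the first administration. Define this reading as baseline for all change scores, use the qualifying scores for eligibility only, and list both readings for each subject. The window of up to 15 days runs from completion of the pre-procedure phase to first administration, so it does not set the interval between the two readings; the protocol gives no limit for that interval.

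**Cost.** About 10 minutes per subject for the THI plus two single ratings, for 10 subjects, and possibly one more short call each. The option of qualifying and completing the pre-procedure evaluation on one day is lost. Completing everything through first use in one day is already unlikely, because "The qualified subject will be shipped a Erchonia® HLS™ device".

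**Limit.** The repeat removes the shift only so far as its errors are independent of the qualifying errors. Placebo response and natural course remain.

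If a repeat is not feasible, state that the qualifying score is the baseline, report the limitation, and show the Week 2 to Week 8 change beside the change from baseline. That later change is free of the shift if errors are independent, but it misses any effect before Week 2. This costs a few lines of text.

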Subjects' identities will be kept confidential by assigning each subject a subject ID upon acceptance into the study. The subject ID will comprise the investigator's two initials (first and last name initials) and a three-digit number that will be based upon the subject's order of entry into the clinical study. For example, with Principal Investigator [name] would have a subject ID of JB101-JB110. Neither the study Sponsor nor Regulatory Insight, Inc. will receive any additional identifying information about a subject and will therefore have no way of linking a subject ID to a particular subject and his or her results.

MONITORING OF THE CLINICAL STUDY

Prior to commencement of the study, the trained study Monitor(s) will provide formalized and documented training to the conduct of clinical studies in general, to the specifics of the current clinical study protocol, to the identification and reporting of adverse events and protocol deviations and to the correct set-up, operation and treatment application of the Erchonia® HLS to the study population for all study staff involved parties. A formalized Clinical Trial Monitoring Plan will be in place for real time, remote and on-site monitoring, as applicable, that will be strictly followed to ensure on-going compliance and accuracy of procedures at the test site(s).

STATISTICAL ANALYSIS

As this is an observational pilot study only, there are no pre-established primary or secondary outcome measures and no pre-established individual subject or study success criteria; rather it is the goal of this study to explore the potential benefits of low level laser therapy administration with the Erchonia HLS™ in reducing symptoms related to tinnitus, the results of which may be used to assist in developing a controlled clinical study to formally evaluate the study goal in the future.

Outcomes Evaluated

The following outcomes will be evaluated as recorded across study duration:

- Tinnitus Handicap Inventory (THI)
- Numerical Rating Scale (NRS): Tinnitus Loudness
- Numerical Rating Scale (NRS): Tinnitus Annoyance
- Satisfaction Rating

Co-Variate Evaluation

Consideration will be given to the role of demographic variables and procedure group assignment.

Evaluation Time Points

Evaluation time points are baseline (pre-treatment), two weeks, four weeks, and 8 weeks study endpoint.

Statistical Procedures

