Outcome data will be presented descriptively and through trending. One-way ANCOVA analysis to evaluate the change in measurements across evaluation points may be applied, as applicable.

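### Change from baseline, and specifically the step from baseline to week 2, may include untreated days that vary by subject, because no THI or NRS score is taken when laser use starts

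*Combined protocol and SAP*

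**What the plan says.** Three timing rules and one analysis rule bear on this point.

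- **Qualifying scores.** Inclusion Criteria Part 2 requires "Total THI score is 38 (Grade 3) or greater" and a score of at least 40 out of 100 on each NRS (annoyance and loudness). These are the only pre-treatment THI and NRS scores that the text lists. The list under Pre-Procedure Evaluation Phase has tinnitus variables, medication and treatment, and demographics.
- **From qualification to first laser use.** The pre-procedure phase "commences following successful study qualification, on the same day or another day", with no upper limit. The Procedure Administration Protocol then says that the laser phase "commences following completion of the pre-procedure phase, on the same day or up to 15 days later".
- **Follow-up.** Ratings are timed by laser use: "Following 2 weeks of study procedure administrations with the Erchonia® HLS™" for the first, with parallel wording at 4 and 8 weeks.
- **Analysis.** The 8 Week Evaluation section says of its data: "These recordings will form the study endpoint data set from which change from baseline will be evaluated". Under Statistical Analysis, "Evaluation time points are baseline (pre-treatment), two weeks, four weeks, and 8 weeks study endpoint", and "Outcome data will be presented descriptively and through trending"; a one-way ANCOVA is optional.

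No section lists a THI or NRS rating on the day of the first session, says which score is the baseline, or describes how the gap is to be reported or handled.

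**The concern.** Baseline and follow-up run on different clocks. Follow-up is counted from the first session. The baseline score belongs to qualification or, at the latest, to the pre-procedure phase. Whatever happens to a subject's score between that rating and the first session is counted as change from baseline and first shows at week 2, where it cannot be told apart from an early response to the laser.

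Two features of the design make this more than a formality. First, subjects enter because their scores are high (THI at least 38, both NRS at least 40). Scores selected in this way may fall on retest without any treatment, and no untreated group shows by how much. Second, a delay after the qualifying scores is likely in practice: qualification is remote, group assignment follows it, and the device is then shipped with a log form for the assigned group. The delay will vary by subject. With 5 subjects per group, assigned by the investigator, it could also differ between Groups A and B, and group is a factor that the plan means to consider.

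At stake is how the week 2 result, and to a lesser degree the week 4 and week 8 changes, will be read when the results are used to help develop a controlled study.

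**Working it through.** **Inputs.** Laser days at the three evaluations are t = 14, 28 and 56 (2, 4 and 8 weeks, from the evaluation sections). The untreated gap from the end of the pre-procedure phase to the first session is g = 0 to 15 days (Procedure Administration Protocol). The step from qualification to the pre-procedure phase is 0 days or more, without limit (Pre-Procedure Evaluation Phase).

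**The plan's own figure.** 8 weeks × 7 daily sessions = 56, which matches the stated total.

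**Laser share of the interval.** Share = t / (t + g).

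| Gap g (days) | Week 2 | Week 4 | Week 8 |
|---|---|---|---|
| 0 | 14/14 = 100% | 28/28 = 100% | 56/56 = 100% |
| 7 | 14/21 = 67% | 28/35 = 80% | 56/63 = 89% |
| 15 | 14/29 = 48% | 28/43 = 65% | 56/71 = 79% |
| 22 (15 + assumed 7) | 14/36 = 39% | 28/50 = 56% | 56/78 = 72% |
| 29 (15 + assumed 14) | 14/43 = 33% | 28/57 = 49% | 56/85 = 66% |

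The last two rows assume a further 7 or 14 days between qualification and the pre-procedure phase; the documents give no figure for that step. A rating labelled week 2 can thus lie 14 days after baseline in one subject and 29 or more in another.

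**Which comparisons are affected.** For one subject, let u be the score change during the gap and L(t) the change from the first session to laser day t.

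- Change from baseline at day t = u + L(t), so u enters at weeks 2, 4 and 8, once each and by the same amount.
- Week 4 minus week 2 = [u + L(28)] − [u + L(14)] = L(28) − L(14), so u cancels.
- Week 8 minus week 4 = L(56) − L(28), so u cancels again.

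The rise from 48% to 79% is therefore the same 15 days over a longer interval, not a changing amount of untreated time.

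**Effect on group means.** The mean change in a group of 5 carries the average of the five values of u, and each subject contributes 1/5 = 20% of it.

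**What cannot be computed.** The documents give no untreated drift, standard deviation or test-retest figure for THI or NRS. The size and sign of u are unknown.

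**The case against.** The strongest reply is that this is a 10-subject, unblinded, uncontrolled pilot with no preset success criteria. Natural course, expectation and regression to the mean would enter change from baseline even with no gap. If untreated drift were linear (an assumption), closing a 15-day gap would remove 15/71 = 21% of that drift from the week 8 change and leave 79%. At week 2 it would remove 15/29 = 52%, but no decision is tied to week 2. This stands as a limit on what the remedy can achieve. It does not make the remedy pointless. A fall after selection need not be linear: some of it may appear at the first rating not used for selection, and a repeat score before the laser would show that part.

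A reader might also infer more than the documents support:

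- *That the course over weeks 2, 4 and 8 is distorted, or that a plateau could be an artefact of the gap.* The gap cancels from those differences and cannot produce a plateau.
- *That 48% is the worst case, or that untreated time is always present.* The step after qualification has no limit, so the share can be lower. A same-day start is allowed, which gives 100%.
- *That the gap can never be recovered.* The Treatment Log Forms document each administration, so the first-session date should be available and the length of the gap can be worked out. Only the score on that day is lost.
- *That the bias must favour the laser.* Retest after selection makes a fall plausible, but scores could drift either way during the gap.
- *That the week 8 rating is really an off-laser rating.* The plan gives no window for that call, but this is ordinary missing detail, and nothing shows that a late call is intended.

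Finally, the text shows a missing figure near the pre-procedure list. If scores are in fact re-recorded in that phase, the unlimited step drops out, but the gap of up to 15 days remains.

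**Conclusion.** The point holds in limited form. As written, the plan allows untreated time between the baseline scores and the first session. Any score change in that time is added in full to every change from baseline and enters through the baseline-to-week-2 step.

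Laser time is 48%, 65% and 79% of the interval at weeks 2, 4 and 8 if two conditions are met: baseline dates from the end of the pre-procedure phase, and the gap is the full 15 days. These are shares of time, not estimates of bias; the bias itself cannot be quantified from the documents.

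For a descriptive pilot this is an inexpensive improvement worth making rather than a flaw that defeats the study.

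**What to change.** Leave the 15-day allowance as it is, and make four changes:

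1. Re-record THI and both NRS remotely just before the first session.
2. Define those scores as the baseline for all change-from-baseline results, and keep the qualifying scores for eligibility only.
3. Take the day 1 date from the Treatment Log Form.
4. Report, by subject and by group, the number of days from qualification to day 1 and the change in score over that time.

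The fourth item gives this uncontrolled study its only view of untreated change.

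The cost is one extra remote completion per subject: the THI, which the protocol puts at 10 minutes, plus two numerical ratings. For 10 subjects the THI time is 10 × 10 = 100 minutes in all. No extra staff or subjects are needed. The new baseline removes only change before laser start. Natural course and expectation after day 1 stay in the results, and the report should say so.
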